Blood pressure will be collected according to a standard protocol. Subjects will be taken to a quiet room with subdued lighting. The appropriate size cuff will be attached to the upper right arm according to the manufacturer's instructions. Blood pressure will be measured three times with a Dinamap Compact Blood Pressure Monitor, which will be programmed to take an initial reading and then a reading after 5 minutes and after 10 minutes. The arm will be adjusted so that the height of the upper arm is level with the heart. Subjects will have both feet flat on the floor. Subjects

will be instructed to refrain from consuming coffee for at least 30 minutes prior to the measurement and will be advised to empty their bladder prior to the measurement. Blood pressure will be obtained at baseline, at 4 weeks, then after 8 weeks of the study. Each measure requires 20 minutes (20 minutes x 3) = 1 hour for the entire study.

**Blood Collection.** Twice during the study, at baseline and after the 8-week treatment period, 25 ml of blood will be collected from the antecubital veins of subjects following an overnight fast. A total of 50 ml of blood will be collected. Plasma and serum will be collected then analyzed. Plasma and serum will be used for analysis of health indices and biomarkers of cardiovascular disease and diabetes (cardiometabolic parameters). Blood will be analyzed for a complete metabolic panel, blood lipids, lipoproteins and inflammation (triglycerides, total cholesterol, HDL cholesterol, LDL cholesterol, and high sensitivity CRP) along with markers of glucoregulatory mechanisms (hemoglobin A1C, fructosamine, insulin, and glucose). Each blood draw requires 20 minutes, (20 minutes x 3) = 1 hour for the entire study.

**Urine Collection.** Twice during the study, at baseline and after the 8-week treatment period subjects will provide a urine sample of at least 10 ml. Urine will be collected in plastic containers and will be stored on ice during collection and until samples can be delivered to the laboratory. Each urine collection requires 5 minutes, (5 minutes x 2) = 10 minutes for the entire study. Urine will be analyzed for urine microalbumin to creatinine ratio.

**Questionnaires.** Participants will be asked to complete a daily questionnaire regarding their general health; if they consumed any over the counter or prescription medications and their general feeling of well-being.

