#### D. Data analysis and sample size justification

Data analysis:

The data will be analyzed using a mixed model in order to partition variance from random and fixed effects. The model will account for age, BMI and the significance for other terms will be tested to determine if they are to remain in the model. Some terms may be used as covariates. Split-plot and split-split plot analysis will be used to partition variances from measurements for which there are repeated measures. Contrasts statements or appropriate multiple comparisons of means will be completed using least-square means.

Sample size:

Sixty males with type 2 diabetes will be recruited for the study. The sample size for this study is based on a standard deviation from a previous study conducted by Basu et al (13), which showed that 50 g of freeze-dried blueberry powder lowered systolic and diastolic blood pressure. A sample size calculation was estimated for a 1-factor ANOVA for a parallel-arm study with > 80% power to detect a significant difference. Twenty-four participants per group are needed, and 30 per group are determined based on a 20% drop out rate.

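### The > 80% power is stated for a 1-factor ANOVA, but section 4.D plans a split-plot mixed model without fixing the treatment contrast or the role of baseline, so the power is not tied to the test that will be run

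*Combined protocol and SAP*

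**What the plan says.** The sample size paragraph of section 4.D (Data analysis and sample size justification) reads: "A sample size calculation was estimated for a 1-factor ANOVA for a parallel-arm study with > 80% power to detect a significant difference". It calls for 24 men per group, raised to 30 for 20% dropout. It refers to an SD from an earlier blueberry study, but gives no value for the SD, the difference or alpha, and does not say which variable the SD belongs to.

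The data analysis paragraph of 4.D describes a different procedure. A mixed model accounts for age and BMI, and "the significance for other terms will be tested to determine if they are to remain in the model". Then: "Some terms may be used as covariates". For repeated measurements, "Split-plot and split-split plot analysis will be used to partition variances from measurements for which there are repeated measures". For the comparisons, "Contrasts statements or appropriate multiple comparisons of means will be completed using least-square means".

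Section 4.A (Procedures) gives the visits. For blood pressure: "Blood pressure will be obtained at baseline, at 4 weeks, then after 8 weeks of the study". For blood markers: "Twice during the study, at baseline and after the 8-week treatment period, 25 ml of blood will be collected".

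**The concern.** With two groups, a 1-factor ANOVA compares one value per man and is equivalent to a two-sample t-test. A split-plot model offers several treatment tests: a main effect averaged over visits, a treatment-by-time interaction, or a difference at a chosen week. Their power differs widely at the same sample size, depending on the correlation between visits and on whether baseline is a covariate, a repeated response or subtracted. Section 4.D names none of these.

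The gap has practical weight. Blood outcomes have only two visits, so if they are analysed as repeated measures, baseline must be one of the responses. A reader cannot tell which test the power statement covers. The choice of contrast, and possibly the retention of treatment-by-time, could also be settled after the data are seen.

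**Working it through.** **Inputs from the plan (4.D, 4.A).** 24 evaluable men per group; 20% dropout; power > 80%; blood pressure at baseline, week 4 and week 8; blood markers at baseline and week 8.

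**Assumed, because the plan is silent.** Two-sided alpha 0.05; SD of level (not of change); equal correlation r between visits of 0.3, 0.6 or 0.8; no group difference at baseline; age and BMI unrelated to outcome.

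**1. The plan's own figure.** 24 / (1 − 0.20) = 30 per group, as stated. The 24 cannot be reproduced without the SD, the difference and alpha.

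**2. Difference implied by 24 per group.** For a two-group ANOVA with 46 error degrees of freedom, noncentrality is n·d²/2. Solving for exactly 80% power at n = 24 gives d = 0.826 SD (24 × 0.826² / 2 ≈ 8.19). The plan says more than 80%, so this is the boundary case.

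**3. Power of other tests at the same n and week 8 difference.**

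- *Two visits, treatment-by-time.* This equals a test of change, with effective difference d / √(2(1 − r)): 0.698, 0.924 and 1.306 at the three correlations.
- *Three visits, treatment-by-time, 2 and 92 df, half the effect at week 4.* The differences are 0, 0.413 and 0.826. Centred, they are −0.413, 0 and 0.413, with sum of squares 0.341. Noncentrality is 12 × 0.341 / (1 − r): 5.85, 10.24 and 20.47.
- *Week 8 adjusted for baseline, age and BMI.* Effective difference d / √(1 − r²): 0.866, 1.033 and 1.377, with 43 error df, averaged over chance imbalance in the three covariates.

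| Test | r = 0.3 | r = 0.6 | r = 0.8 |
|---|---|---|---|
| 1-factor ANOVA on week 8 values | 80% | 80% | 80% |
| Treatment-by-time, two visits | 66% | 88% | 99% |
| Treatment-by-time, three visits, half effect at week 4 | 56% | 81% | 98% |
| Week 8 adjusted for baseline, age, BMI | 81% | 92% | 99% |

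The two-visit interaction reaches 80% only at r = 0.5. The three-visit version has 71% there. The adjusted week 8 test falls to about 77% to 79% at r from 0 to 0.2. If the borrowed SD is of change instead, the adjusted test has 92%, 86% and 81% at the three correlations, and 79% at 0.9.

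**4. Conditional illustrations only.**

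- Suppose treatment-by-time were subject to the retention rule, and either it or the treatment main effect could carry the claim. In a balanced split-plot with equal correlations the two tests are independent, so the false-positive rate per outcome would be 1 − 0.95² = 9.75%. Null simulations gave 9.6% to 9.9%.
- Suppose a treatment average that includes baseline were the sole test. With two visits the effective difference is (d/2) / √((1 + r)/2): 0.512, 0.462 and 0.435. Power would be 41%, 35% and 31%.

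**The case against.** Sizing on a simple two-group test and then analysing with a richer model is common. The plan permits a baseline covariate and week-specific contrasts, and under that reading power is about 80% or better at moderate correlations. That stands: nothing here shows that 24 per group is too few.

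A reader might infer that the false-positive rate is doubled. The documents do not support this. In 4.D the sentence about testing other terms follows age and BMI and precedes the remark about covariates, so it can naturally be read as covariate screening. The plan never says that either of two treatment tests may carry a claim, and its reference to appropriate multiple comparisons may include adjustment. The 9.75% is therefore an illustration. What remains is that no sentence protects treatment-by-time from the retention rule.

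A reader might also infer that the sizing used a blood pressure SD. The plan says that the cited study lowered blood pressure, not which variable supplied the SD.

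Two features are not faults. The dropout arithmetic is correct. Split-split plot can be read as covering the readings within a visit, since "Blood pressure will be measured three times with a Dinamap Compact Blood Pressure Monitor". A model with baseline as a response and equal baseline means would also be valid. The objection is only to averaging baseline into the treatment effect, or leaving its role open.

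**Conclusion.** The concern holds as a gap in specification: the stated power is not tied to the test that will be run. At a fixed sample size and week 8 difference, ordinary tests that 4.D allows range from 56% to 99% power at correlations of 0.3 to 0.8, against 80% for the ANOVA. The low end is not confined to unusual choices, because a sole treatment-by-time test falls below 80% at correlations under about 0.5.

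A reader might conclude that the trial is underpowered. The documents do not support that: a permitted analysis, the adjusted week 8 difference, has 81% to 99% over the same range. The 31% to 41% figures belong to a sole test that the plan neither states nor rules out.

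Apart from the 24 per group, every input to these power figures is an assumption, so confidence in the sizes is moderate. The gap itself is read directly from 4.D, and no other section closes it. It should be corrected, but it does not undermine the design.

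**What to change.** Add to section 4.D, before unblinding:

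> For each outcome the treatment effect is the between-group difference at week 8, adjusted for the baseline value of that outcome, age and baseline BMI (baseline BMI omitted where the outcome is body weight or BMI). Baseline is used for adjustment and not averaged into the treatment effect. Treatment and, where there is more than one post-baseline visit, treatment-by-visit terms are kept whatever their significance; significance-based selection does not apply to them.

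Week 8 is the only post-baseline visit shared by blood pressure and the blood outcomes. BMI must be the baseline value because weight is measured again at weeks 4 and 8.

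Also state which endpoint and which SD (of level or of change) the sample size used, and restate the power for this test. The restatement should not promise 80% at every correlation: it is about 77% to 79% if baseline correlates weakly (0 to 0.2) with the outcome.

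**Cost.** Text only: no extra participants or visits, and sample size unchanged. Three covariates leave 43 error degrees of freedom instead of 46, the power figure is slightly less favourable at weak correlation, and a week 4 blood pressure effect is not pooled into the main test. The change does not address multiplicity across outcomes.

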### **5. RISK/BENEFIT ASSESSMENT:**

This study has a minimal level of risk. Blood collection may cause a small amount of pain when the needle is inserted into the vein. Sometimes, after blood is taken, a small bruise can appear at the site. This bruise, however, does not cause any long-term problems. Aside from the discomfort of the needle puncture, there is nothing in this procedure that can cause any problem. There is also a remote chance of fainting, light-headedness, or infection. Blood will be drawn from a forearm vein by a trained

professional using sterile, disposable material.

To minimize the risk of bruising and pain, skilled and experienced phlebotomists will collect blood samples. If during the study, a participant ever experiences vertigo, he will thereafter have his blood drawn while reclining in a suitable chair (during subject selection, participants are asked if they have or had a history of fainting while giving blood).

## **6. STUDY POPLUATION – GENDER/ETHNIC INCLUSION:**

Rationale for research subject selection – The population from which participants will be recruited consists of approximately 5000 individuals receiving care for type 2 diabetes living within commuting distance of the study site at the Stratton VA Medical Center, Albany, NY.

